8.3.2 Severity

The Investigator is responsible for assessing the severity (intensity) of each adverse event as mild, moderate, or severe according to the following definitions:

Mild – An event that is easily tolerated and generally not interfering with normal daily activities. Moderate – An event that is sufficiently discomforting to interfere with normal daily activities. Severe – An event that is incapacitating with inability to work or perform normal daily activities. It should be noted that a severe AE need not be serious and that a serious adverse event (SAE) need not, by definition, be severe.

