5.4 Participant Withdrawal

All participants have the right to withdraw from this study at any time. In addition, it is the right of the Investigator to remove participants from the study as a result of adverse reactions, a protocol violation, or non-compliance, or any other reason. Participants must be discontinued for the following reasons:

- Participant withdraws consent or requests discontinuation from the study for any reason;
- Occurrence of a medical condition or circumstance that exposes the participant to substantial risk and/or does not allow the participant to adhere to the requirements of the protocol as determined by the Investigator;
- Any serious adverse event (SAE), clinically significant adverse event, severe laboratory abnormality, concomitant illness, or other medical condition which indicates to the Investigator that continued participation is not in the best interest of the participant;
- Requirement for prohibited concomitant medication;
- Termination of the study by the Sponsor or the regulatory authority.

Should a participant withdraw after administration of EM in Period 1, or should the Investigator decide to withdraw the participant, all efforts will be made to complete and report the protocolstipulated observations up to the time of withdrawal. Week 16 procedures (see Section 10.3.5 and Section 14.1 Schedule of Study Assessments) will be completed at the time of the participant's withdrawal and an explanation provided as to why the participant is withdrawing or being withdrawn from the study.

In a case of participants lost to follow-up, attempts to contact the participant must be made and documented in the participant's medical records.

The Investigator must document the primary reason for discontinuation of a study participant on the appropriate case report form (CRF). If the reason for withdrawal is a clinical AE, monitoring will continue until the AE resolves or the Investigator assesses the AE as chronic and stabilized.

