8 EVALUATION AND REPORTING OF ADVERSE EVENTS

8.1 Adverse Events

An adverse event is defined as any untoward medical occurrence in a clinical investigation participant administered a pharmaceutical product, which does not necessarily have a causal relationship with this treatment. An adverse event can therefore be any unfavorable and/or unintended sign (including an abnormal laboratory finding), symptom, or disease temporally associated with the use of an investigational medicinal product, whether or not related to the investigational medicinal product. All adverse events, including observed or volunteered problems, complaints, or symptoms, are to be recorded on the appropriate CRF.

Adverse events, which include abnormal and clinically significant clinical laboratory test variables, will be monitored and documented from the time Informed Consent until study participation is

complete (the Follow-up Visit). Participants should be instructed to report any adverse event that they experience to the Investigator. Beginning with the signing of the informed consent until the time of the first dose of study drug, investigators should make updates to medical history and record any pre-existing medical condition or signs or symptoms that changes in severity, frequency, or seriousness in the medical history. Serious adverse events that occur prior to the first dose of study drug should be reported as an update to medical history as well as be reported on the appropriate adverse event CRF.

Beginning with the first dose of study drug, investigators should make an assessment for adverse events at each visit and record all adverse events, non-serious and serious, on the appropriate adverse event CRF.

Wherever possible, a specific disease or syndrome rather than individual associated signs and symptoms should be identified by the Investigator and recorded on the CRF. However, if an observed or reported sign or symptom is not considered a component of a specific disease or syndrome by the Investigator, it should be recorded as a separate adverse event on the CRF. Additionally, the condition that led to a medical or surgical procedure (e.g., surgery, endoscopy, tooth extraction, or transfusion) should be recorded as an adverse event, not the procedure. Concomitant procedures should be recorded as such on the appropriate CRF.

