10.5 Safety Analysis

Safety analysis will be based on all participants receiving at least one dose of study medication. Treatment emergent AEs will be summarized based on the frequency of AEs and their severity for all dosed participants. Adverse Events (AEs), including clinically meaningful laboratory abnormalities and significant behavioral changes, will collected. AE severity and relatedness to treatment will be assessed. AEs will be tabulated for placebo and BPN14770 treatments using preferred terms and system organ classes. Summaries will also be provided by severity and relationship to treatment. Serious Adverse Events (SAEs) will be summarized separately, in a manner similar to that used for Adverse Events.

Overall safety and tolerability will be assessed by clinical and/or statistical review of all safety parameters including adverse experiences, laboratory values, vital signs, physical exams, and ECG data. General clinical and laboratory adverse events will be presented in frequency tables. Summary statistics (n, mean, SD, median, and range (minimum, maximum) will be tabulated for the observed values and the change (or percent change) from baseline for all continuous parameters for vital signs and laboratory tests.

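### Section 8.3.2 grades adverse events only by tolerance and lost daily function, so a symptom-free laboratory or vital-sign event can be graded no higher than Mild, whatever its size

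*Combined protocol and SAP*

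**What the plan says.** Section 8.3.2 sets one scale for all events: "The Investigator is responsible for assessing the severity (intensity) of each adverse event as mild, moderate, or severe according to the following definitions". The three grades are:

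- Mild: the participant tolerates it easily and daily life is largely undisturbed.
- Moderate: "An event that is sufficiently discomforting to interfere with normal daily activities"
- Severe: the participant is incapacitated and cannot work or cannot carry on his usual daily life.

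No other severity criterion appears in the protocol.

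Laboratory findings fall within the scale. Section 8.1 says: "Adverse events, which include abnormal and clinically significant clinical laboratory test variables, will be monitored and documented". Section 10.5 describes the events to be collected as "including clinically meaningful laboratory abnormalities and significant behavioral changes". The general definition in 8.1 also covers any unfavourable or unintended sign, so a change in blood pressure or pulse can be an adverse event.

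Both the synopsis (Safety Analyses) and 10.5 promise summaries of adverse events by severity. Section 7.9 asks the investigator whether an out-of-range result is a clinically significant change from baseline, but sets no grade of size. Section 5.4, on withdrawal, lists among its reasons a "clinically significant adverse event, severe laboratory abnormality, concomitant illness" and does not define what makes a laboratory abnormality severe.

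**The concern.** The scale measures how an event is felt and what it stops the participant doing. That suits headache or nausea. It does not suit a raised liver enzyme, a low platelet count or a blood-pressure change found at a scheduled visit, whose importance lies in the size of the value.

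Safety and tolerability is one of the three objectives in 3.4.1. Two of the three safety endpoints in 3.4.3 are vital signs and laboratory evaluations. If the severity table cannot separate a small symptom-free departure from a large one, it says nothing about severity for events arising from those two endpoints. A reader who finds no Moderate or Severe laboratory events could take this as evidence about the treatments, when the definitions alone would produce it.

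**Working it through.** No arithmetic applies. The plan gives no adverse event rate, no grading thresholds and no figure to reproduce. The check is to apply the three definitions in 8.3.2, as written, to the kinds of event that 8.1 and 10.5 admit.

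| Event | Interferes with daily activities? | Incapacitating? | Grade under 8.3.2 |
|---|---|---|---|
| Clinically significant laboratory value, modest departure, no symptoms | No | No | Mild |
| Clinically significant laboratory value, large departure, no symptoms | No | No | Mild |
| Vital-sign change recorded as an event, no symptoms | No | No | Mild |
| Laboratory abnormality with symptoms that disrupt the day | Yes | Depends | Moderate or Severe |
| Behavioural change that disrupts daily activities | Yes | Depends | Moderate or Severe |

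Step by step:

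1. Section 8.3.2 requires a grade for each adverse event, so a laboratory event cannot be left ungraded.
2. Moderate needs discomfort that interferes with activities. A symptom-free finding causes neither discomfort nor interference, so Moderate is excluded.
3. Severe needs incapacity, which is also excluded.
4. Only Mild remains. The size of the value enters none of the definitions, so the first two rows cannot be told apart.
5. In the severity summaries promised by the synopsis and 10.5, the Moderate and Severe cells are therefore empty by rule for symptom-free laboratory and vital-sign events, in every treatment period.

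What does not depend on the grade:

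- Section 10.5 gives n, mean, SD, median and range for observed values and change from baseline, for continuous laboratory and vital-sign parameters. An extreme value appears there as a minimum or maximum.
- Section 8.2.3 judges seriousness separately and names blood dyscrasias among its examples of important medical events. Section 8.3.2 itself says that a serious event need not be severe. A symptom-free blood dyscrasia could thus be reported as serious and still be tabulated as Mild.

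On 5.4: the withdrawal list uses the word severe for a laboratory abnormality. Under 8.3.2 a symptom-free result cannot earn that word, and no other section gives it a meaning.

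**The case against.** The strongest reply is that little is lost. The numeric summaries in 10.5 show extreme values, the serious-event rules catch the dangerous ones, 7.9 has the investigator review every laboratory result, and this is a descriptive study of 15 men. Most of this stands, and it confines the effect to the severity tables. It does not remove it. The numeric summaries do not link a value to an adverse event or its grade, and they cover continuous parameters only, so urinalysis results reported as categories are outside them.

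A second reply is that Mild is not forced: the text does not say how toleration applies to a large abnormality, so the investigator would use judgement. But an event that fits none of the definitions must still be graded, and the protocol offers no rule for doing so. Under 6.4 the investigator knows the treatment, and under 4.1 every participant takes the same sequence, so unwritten discretion is a weak substitute.

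A third reply is that 5.4 does not contradict 8.3.2, because it lists the laboratory abnormality apart from the clinically significant adverse event and leaves the decision to the investigator. That is fair. What remains is an undefined term that shares a word with a defined grade.

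Three stronger readings are tempting, and the documents do not support them:

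- A reader might infer that behavioural events are understated too. They are not capped at Mild: the Severe definition covers loss of normal daily activities as well as work, so disruptive behaviour can be graded Moderate or Severe. Section 8.3.2 does not say that function is judged against the participant's usual state, but an error from that could go either way.
- A reader might read 10.5 as singling out vital signs. Its sentence names laboratory abnormalities and behavioural changes. Vital signs enter through the general definition in 8.1.
- A reader might size the problem by counting measurements: 37 analytes × 4 panels × 15 men = 2,220 results, and 4 vital signs × 4 visits × 15 = 240 readings. These are scheduled measurements, not events. Under 8.1 a laboratory event must be clinically significant, and an abnormality not confirmed on repeat need not be reported.

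**Conclusion.** The point holds for symptom-free laboratory and vital-sign adverse events. Applied as written, 8.3.2 gives them one grade out of three, whatever the size of the value. This is a stated rule that gives an uninformative grade, and not merely a missing detail.

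The effect is limited to the tables of adverse events by severity. Numeric summaries, the classification of serious events and the judgement of clinical significance are untouched. How many events would be affected is unknown, because the documents give no rate of laboratory or vital-sign events. It would therefore be wrong to forecast that the trial will report mostly mild events because of this rule.

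The conclusion assumes that investigators grade by the written definitions and that at least one such event occurs without symptoms. If no such event occurs, the defect has no practical effect. If investigators depart from the definitions, the grades follow no stated rule.

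**What to change.** In 8.3.2, keep the present wording for symptomatic events and add a sentence to this effect: laboratory and vital-sign adverse events are graded by the size of the value, with or without symptoms, on a published numerical scale named in the protocol, with its levels mapped to mild, moderate and severe. State also how a finding is graded when the chosen scale has no numerical level for it, as may happen with some urinalysis results.

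Reconcile the term for severe laboratory findings in 5.4 with the definition adopted, by cross-reference or by different wording. Which findings should lead to withdrawal is a clinical matter, and this point takes no position on it.

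The cost is choosing and mapping a scale, a line in the CRF instructions, and amendment review under 12.5. No new data are needed, because the values are already collected at each period-end visit. Some events will move to a higher grade, so the severity table may look less favourable.

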8.3.3 Adverse Event Monitoring and Follow-up

Participants who experience AEs will be monitored with relevant clinical assessments and laboratory tests, as determined by the Investigator. In accordance with good medical practice, all AEs must be followed to satisfactory resolution or stabilization of the event(s), or, if a chronic condition, until fully characterized. Any actions taken and follow-up results must be recorded either on the appropriate page of the CRF, as well as in the participant's source documentation. Follow-up laboratory results should be filed with the participant's source documentation.

For all AEs that require the participant to be discontinued from the study, relevant clinical assessments and laboratory tests must be repeated at appropriate intervals until final resolution or stabilization of the event(s).

Participants who have non-serious AEs that are ongoing at study completion or study withdrawal must be followed until resolution of the AEs or for 30 days after the last dose of study drug, whichever comes first. Participants who have an ongoing SAE at study completion or study withdrawal must be followed until the event resolves or the event or sequela stabilizes.

SAE documentations will include: Investigator details (name, phone, fax, e-mail) Participant number Participant demographics (age, date of birth, sex, weight) Clinical event

- Description
- \circ Date of onset
- Treatment (drug, dose, dosage form)
- AE relationship to study drug
- Action taken regarding study drug in direct relationship to the AE

If the AE was fatal or life-threatening Cause of death (whether or not the death was related to study drug) Autopsy findings (if available)

The Investigator must continue to follow the participant until the SAE has subsided or until the condition becomes chronic in nature, stabilizes (in the case of persistent impairment), or the participant dies. Within 24 hours of receipt of follow-up information, the Investigator must update the Sponsor and submit any supporting documentation (e.g., participant discharge summary or autopsy reports).

Any new SAE that occurs within one month after the study period and is considered to be possibly related to the investigational product should be recorded and reported immediately to the Sponsor. The clinical research site will be responsible for reporting SAEs to the Institutional Review Board (IRB) per FDA regulations.

9 STUDY PROCEDURES AND ASSESSMENTS BY VISIT

9.1 Schedule of Assessments

The study timetable in Section 14.1 shows the schedule of planned study procedures. Every effort should be made to adhere to this procedure schedule.

9.2 Screening (Day -28 to Day -1)

The study will consist of a Screening period of 28 days or less. Screening and Baseline visits may be combined.

Each potential study participant will have the following assessments completed by the Investigator or designee up to 28 days prior to the first dose of study medication:

- Obtain informed consent;
- Obtain medical/surgical history;
- Obtain demographics and social history (tobacco, alcohol, and/or drug use);
- Obtain prior/concomitant medication use;
- Conduct full physical exam;
- Obtain height and weight;
- Obtain vital signs;
- Draw blood samples for Chemistry and Hematology;
- Collect urine for safety urinalysis;
- Complete Stanford-Binet assessment;
- Evaluate inclusion and exclusion criteria.

9.3 Baseline (Period 1/Day 1)

Participants will return to the clinic for the Period 1/Day 1 Visit (Baseline) following successful screening. If clinic processes allow, the Screening and Baseline visits may be combined; in this case, it is not necessary to repeat vital signs nor to conduct the abbreviated physical exam.

9.3.1 **Prior to Drug Dispensing**

The following assessments will be completed:

- Conduct abbreviated physical exam (not to be repeated if the Screening and Baseline visits occur on the same day);
- Obtain vital signs (not to be repeated if the Screening and Baseline visits occur on the same day);
- Record any updates to medical/surgical history;
- Record any updates to prior/concomitant medication use;
- Re-evaluate inclusion and exclusion criteria based on preceding activities;
- Verify continued eligibility;
- Complete baseline cognitive, behavioral and pharmocodynamic assessments:
 - NIH Toolbox Cognitive Battery for Intellectual Disabilities (NIH-TCB)
 - Test of Attentional Performance (KiTAP)
 - Clinical Global Impression Severity Investigator rated (CGI-S)
 - Visual Analog Scale (VAS) assessment of participant-specific behavioral anchors
 - Aberrant Behavior Checklist (ABC)
 - Anxiety, Depression, and Mood Scale (ADAMS)
 - Vineland-3 Rating Scale
 - Event-Related Potentials (ERP)
 - Eye Tracking

If participant remains eligible for the study:

• Dispense study medication.

9.3.2 Weeks 1, 5, 9, 13 (Periods 1 through 4)

The following assessments will be completed at the Week 1 Visit during each Period:

- Telephone call to:
 - Record any updates to concomitant medication use
 - Assess and record any adverse events.

9.3.3 Week 4, 8, 12, 16 (end Periods 1 through 4)

The following assessments will be completed at the Week 12 Visit during Periods 1 and 2:

- Collect weight;
- Collect vital signs;
- Draw blood samples for Chemistry and Hematology;
- Collect urine for safety urinalysis;
- Conduct the following cognitive, behavioral and pharmocodynamic tests:
 - NIH Toolbox Cognitive Battery for Intellectual Disabilities (NIH-TCB)
 - Test of Attentional Performance (KiTAP)
 - Clinical Global Impression Severity Investigator rated (CGI-S)

- Clinical Global Impression Improvement Investigator rated (CGI-I)
- Visual Analog Scale (VAS) assessment of participant-specific behavioral anchors
- Aberrant Behavior Checklist (ABC)
- Anxiety, Depression, and Mood Scale (ADAMS)
- Vineland-3 Rating Scale
- Event-Related Potentials (ERP)
- Eye Tracking
- Collect study medication and record capsule count remaining in bottle to assess dosing compliance;
- Record any updates to concomitant medication use; and
- Assess and record any adverse events.

9.3.4 Week 17 (Period 4, Final Contact at End of Study)

- Telephone call to:
 - Record any updates to concomitant medication use,
 - Assess and record any adverse events, and
 - Record final participant disposition.

9.3.5 Early Termination

It is hoped that all participants can be followed through to the conclusion of the study at Period 4/Week 17. However, if an early termination occurs, the Week 16 procedures should be completed at the time of the participant's withdrawal (if possible) and an explanation provided as to why the participant is withdrawing or being withdrawn from the study. Procedures to be completed early termination:

- Collect weight;
- Collect vital signs;
- Draw blood samples for Chemistry and Hematology;
- Collect urine for safety urinalysis;
- Conduct the following cognitive tests:
 - NIH Toolbox Cognitive Battery for Intellectual Disabilities (NIH-TCB)
 - Test of Attentional Performance (KiTAP)
 - Clinical Global Impression Severity Investigator rated (CGI-S)
 - Clinical Global Impression Improvement Investigator rated (CGI-I)
 - Visual Analog Scale (VAS) assessment of participant-specific behavioral anchors
 - Aberrant Behavior Checklist (ABC)
 - Anxiety, Depression, and Mood Scale (ADAMS)
 - Vineland-3 Rating Scale
 - Event-Related Potentials (ERP)
 - Eye Tracking
- Collect study medication and record capsule count remaining in bottle to assess dosing compliance;
- Record any updates to concomitant medication use;
- Assess and record and adverse events; and
- Record final participant disposition.

10 PLANNED STATISTICAL METHODS

10.1 Sample Size

Given the exploratory nature of this study, a definitive sample size calculation is not possible.

10.2 Demographics

Summary statistics [number (n), mean, standard deviation (SD), minimum, median, and maximum] will be tabulated for the observed values for all continuous demographic parameters. Frequencies and percentages will be tabulated for categorical data.

10.3 Analysis Populations

The primary efficacy population will be the intent to treat (ITT) efficacy population, which will include all randomized participants who received at least one dose of treatment and returned for at least one follow-up visit. The completers population (CP), defined as all randomized participants who completed all treatment periods with no significant protocol violations, will be used to evaluate the robustness of the ITT results.

The Safety population will include all randomized participants who received at least one dose of study treatment.

10.4 Efficacy: Cognitive, Behavioral and Pharmocodynamic Measures Analysis

All cognitive and behavioral parameters will be summarized at each time point collected and standard descriptive statistics provided. Baseline measurements are defined as those obtained on Day 1/Period 1 prior to receipt of any study medication. For cognitive parameters measured at baseline, change from baseline will also be calculated and standard descriptive statistics provided for each time point.

